3.3. Strata and Covariates

No covariates will be included in efficacy analyses.

3.4. Examination of Participant Subgroups

There are no prespecified participant subgroups for efficacy or safety analyses.

3.5. Multiple Comparisons

Adjustments for multiplicity will not be made, because no formal statistical testing will be performed in this study.

3.6. Missing Data and Outliers

3.6.1. Missing Data

In general, missing data will not be imputed unless methods for handling missing data are specified. Exceptions are presented in this document.

The handling of missing or incomplete dates for AE start is described in Section 7.1.6.2, and for prior and concomitant medications in Section 7.4.

3.6.2. Outliers

Outliers will be identified during the data management and data analysis process, but no sensitivity analyses will be conducted. All data will be included in the data analysis.

3.7. Data Handling Conventions and Transformations

The following conventions will be used for the imputation of date of birth when it is partially missing or not collected:

- If only month and year of birth is collected, then “15” will be imputed as the day of birth
- If only year of birth is collected, then “01 July” will be imputed as the day and month of birth
- If year of birth is missing, then date of birth will not be imputed.

In general, age collected at Day 1 (in years) from the demographics eCRF will be used for analyses and presented in listings. If age at Day 1 is not available for a participant, then age derived based on date of birth and the Day 1 visit date will be used instead. If a randomized participant was not dosed with any study drug, the randomization date will be used instead of the Day 1 visit date. For screen failures, the date the first informed consent was signed will be used for the age derivation. Age required for longitudinal and temporal calculations and analyses (e.g., age on date of laboratory assessment) will be based on age derived from date of birth and the date of the measurement or event, unless otherwise specified.

Data that are continuous in nature but are less than the lower limit of quantitation (LOQ) or above the upper LOQ will be imputed as follows:

- A value that is 1 unit less than the lower LOQ at the same precision level of the originally reported value will be used to calculate descriptive statistics if the datum is reported in the form of “ $< x$ ” (where x is considered the lower LOQ). For example, if the values are reported as < 50 and < 5.0 , values of 49 and 4.9, respectively, will be used to calculate summary statistics. An exception to this rule is any value reported as < 1 or < 0.1 , etc. For values reported as < 1 or < 0.1 , a value of 0.9 or 0.09, respectively, will be used to calculate summary statistics.

- A value that is 1 unit above the upper LOQ will be used to calculate descriptive statistics if the datum is reported in the form of “> x” (where x is considered the upper LOQ). Values with decimal points will follow the same logic as above.
- The lower or upper LOQ will be used to calculate descriptive statistics if the datum is reported in the form of “≤ x” or “≥ x” (where x is considered the lower or upper LOQ, respectively).

If methods based on the assumption that the data are normally distributed are not adequate, analyses may be performed on transformed data or nonparametric analysis methods may be used.

3.8. Visit Definitions

3.8.1. Definition of Baseline, Postbaseline, Study Day, and Follow-Up Day

Baseline is defined as the last available value collected on or prior to the first dose date (and time, where applicable) of investigational product (i.e., prior to taking first dose of investigational product).

Postbaseline is defined as any value collected after the first dose of investigational product.

Study day will be calculated from the first dosing date of investigational product and derived as follows:

- For postdose study days: Assessment Date – First Dosing Date + 1
- For days prior to the first dose: Assessment Date – First Dosing Date

Therefore, study day 1 is the day of first dose of investigational product.

Last Dose Date is defined as the date of the last injection of GS-2829 or GS-6779 [or PBO].

Follow-Up (FU) Day will be calculated from the last dosing date of investigational product and will be derived as follows:

- Assessment date – Last Dose Date

Both Study Day and FU Day will be displayed in listings of data for endpoints remapped to FU visits in Table 3-1 to Table 3-4 in Section 3.8.2 (when possible).

Last Study Date is the latest of clinic visit dates and laboratory visit dates, including all follow-up visits for participants who prematurely discontinued study or who completed study according to the Study Completion eCRF.

Day 15	Day 15	Day 15 [#]	Day 15 [#]
Day 29	Day 29* ^{\$}	Day 29*# ^{\$}	Day 29*# ^{\$}
Day 43	–	Day 43	Day 43
Day 57	Day 57* ^{\$}	Day 57*# ^{\$}	Day 57*# ^{\$}
Day 71	FU-WK2	Day 71	Day 71
Day 85	FU-WK4^{\$}	Day 85*# ^{\$}	Day 85*# ^{\$}
Day 99	–	FU-WK2	Day 99
Day 113	–	FU-WK4*#^{\$}	Day 113*# ^{\$}
Day 127	–	–	Day 127
Day 141	FU-WK12^{\$}	–	Day 141*# ^{\$}
Day 155	–	–	FU-WK2
Day 169	–	FU-WK12*#^{\$}	FU-WK4*#^{\$}
Day 225	FU-WK24*^{\$}	–	FU-WK12*#^{\$}
Day 253	–	FU-WK24*#[#]	–
Day 309	–	–	FU-WK24*#[#]

*Creatinine Clearance (estimated using Cockcroft-Gault method) collected at this subset of visits.

#Viral biomarkers (HBV DNA, quantitative HBsAg, anti-HBsAg antibody, HBcrAg, HBeAg and anti-HBeAg antibody) collected at this subset of visits for participants in Cohorts 5, 6, and 7 (only).

\$ Antibody to HBsAg [Phase 1a participants only].

Table 3-2. Remapped Follow-Up Visits for Vital Signs, Weight, and BMI

Nominal Visit	Cohorts 1, 2	Cohorts 3, 4, 5, 6	Cohorts 7, 8
Last Value prior to first dose date=Baseline	Baseline*#	Baseline*#	Baseline*#
Day 8	Day 8	–	–
Day 15	Day 15	Day 15	Day 15
Day 29	Day 29	Day 29*#	Day 29*#
Day 43	–	Day 43	Day 43
Day 57	Day 57*#	Day 57*#	Day 57*#
Day 64	FU-WK1	–	–
Day 71	FU-WK2	Day 71	Day 71
Day 85	FU-WK4	Day 85*#	Day 85*#
Day 92	–	FU-WK1	–
Day 99	–	FU-WK2	Day 99
Day 113	–	FU-WK4	Day 113*#
Day 127	–	–	Day 127
Day 141	FU-WK12	–	Day 141*#
Day 148	–	–	FU-WK1
Day 155	–	–	FU-WK2
Day 169	–	FU-WK12	FU-WK4
Day 225	FU-WK24*	–	FU-WK12
Day 253	–	FU-WK24*	–
Day 309	–	–	FU-WK24*

*Weight (and the calculation of BMI) performed at this subset of the visits.

“Pre-dose” and “Post-dose” timepoints will be displayed for vital signs that were collected on injection days.

Table 3-3. Remapped Follow-Up Visits for IFNy ELISpot Assay

Nominal Visit	Cohorts 1, 2	Cohorts 3, 4, 5, 6	Cohorts 7, 8
Last Value prior to first dose date=Baseline	Baseline	Baseline	Baseline
Day 15	Day 15	Day 15	–
Day 29	Day 29	Day 29	–
Day 43	–	Day 43	–
Day 57	Day 57	Day 57	Day 57
Day 71	FU-WK2	Day 71	Day 71
Day 85	FU-WK4	Day 85	Day 85
Day 99	–	FU-WK2	Day 99
Day 113	–	FU-WK4	Day 113
Day 127	–	–	Day 127
Day 141	FU-WK12	–	Day 141
Day 155	–	–	FU-WK2
Day 169	–	FU-WK12	FU-WK4
Day 225	FU-WK24	–	FU-WK12

Table 3-4. Remapped Follow-Up Visits for ECGs

Nominal Visit	Cohorts 1, 2	Cohorts 3, 4, 5, 6	Cohorts 7, 8
Last Value prior to first dose date=Baseline	Baseline	Baseline	Baseline
Day 85	–	Day 85	Day 85
Day 141	–	–	Day 141
Day 225	FU-WK24	–	–
Day 253	–	FU-WK24	–
Day 309	–	–	FU-WK24

Note: Day 85 is after 2 cycles of injections; Day 141 is after 3 cycles of injections.

4. PARTICIPANT DISPOSITION

4.1. Participant Randomization and Disposition

Key study dates (ie, first participant screened, first participant randomized, last participant randomized, last participant last visit for the primary endpoint, and last participant last visit for the clinical study report) will be provided separately for each population (healthy participants [phase 1a] and virally suppressed CHB participants [phase 1b]).

A summary of participant randomization into this study will be provided separately for each population (healthy participants [phase 1a] and virally suppressed CHB participants [phase 1b]). Displays will be presented by treatment group (active participants within each cohort followed by all participants assigned to placebo [within population]) and overall for all participants in the population for each country, and investigator within country. The denominator for the percentage calculation will be the total number of participants randomized for that column.

The randomization schedule used for the study will be provided.

A summary of participant disposition will be provided separately for each population (healthy participants [phase 1a] and virally suppressed CHB participants [phase 1b]) for the All Randomized Analysis Set. Displays will be by treatment group (active participants within each cohort followed by all participants [within population] assigned to placebo) and overall for all participants in the population. The denominator for the percentage calculation for completion status and reasons for premature discontinuation will be the total number of participants in the Safety Analysis Set for each column. The number and percentage of participants in each of the categories listed below will be summarized:

- All Randomized Analysis Set
- All Randomized but Never Dosed
- Safety Analysis Set
- Completed study drug
- Did not complete study drug with reasons for premature discontinuation of study drug
- Completed study
- Did not complete the study with reasons for premature discontinuation of study

For the status of study drug and study completion and reasons for premature discontinuation, the number and percentage of participants in each category will be provided. In addition, a flowchart for each of the participant populations will be provided to depict the disposition.

The following by-participant listings will be provided separately for each participant population to support the above summary tables:

- Reasons for screen failure (will be provided by screening ID number in ascending order)
- Analysis set status (participants excluded from any of the analysis sets)
- Participants who prematurely discontinued any of the study drugs

By-participant listings of disposition including cohort, treatment group, date of the last dose of study drug (study days), study drug completion status, reason for study drug discontinuation, study completion status, and reason for study discontinuation will be produced for each of the 2 participant populations.

4.2. Extent of Study Drug Exposure

For each participant, the number of injections received for each type of vector (GS-2829 and/or GS-6779) and dose level (high dose or low dose for participants receiving active treatment) or placebo for each vector will be calculated. For each population and treatment group (active participants within each cohort followed by all participants [within population] assigned to placebo), the number of participants taking 0, 1, 2, or 3 doses of the vector and dose level combination or placebo for the vector will be provided. Dosing information will be summarized based on data collected on the Study Drug Administration eCRF. Subjects who took only one of the vectors (eg, GS-2829 in Cohort 1 and GS-6779 in Cohort 2) will have 0, 1, or 2 injections for the vector administered/Low Dose or placebo for the vector. Cohorts 3 to 8 will have the number of injections received (0, 1, 2, or 3) for each of the following categories:

- GS-2829 Low Dose
- GS-2829 High Dose
- GS-2829 Placebo
- GS-6779 Low Dose
- GS-6779 High Dose
- GS-6779 Placebo

A by-participant listing of study drug administration will be provided separately for each participant population. Sort order will be as described in Section 3 of this SAP.

4.3. Protocol Deviations

Protocol deviations occurring after participants entered the study are documented during routine monitoring. The number and percentage of participants with at least 1 important protocol deviation (IPD) will be summarized by treatment group for the All Randomized Analysis Set. The following subcategories will also be displayed by treatment group:

- Number of IPDs for each participant (1, 2, or 3 or more IPDs)
- Total Number of Important Protocol Deviations
Note: A participant may be counted across multiple important protocol deviation categories.

A by-participant listing will be provided for those participants with protocol deviations. The listing of protocol deviations (IPDs and non-IPDs) will include a column to specify whether the protocol deviation is an IPD.

Participants who did not meet eligibility criteria for study entry but were enrolled will be listed separately for each population.

4.4. Assessment of Disaster or Public Health Emergency Impact

This study was ongoing during the novel coronavirus (COVID-19) pandemic which had an impact on the study conduct. Some participants were unable to attend onsite visits due to shelter in place guidelines, site closures, or other reasons. This section describes how special situations due to COVID-19 will be handled in the analysis.

4.4.1. Study Drug or Study Discontinuation Due to Disaster or Public Health Emergency

A by-participant listing of reasons for premature study drug or study discontinuation due to COVID-19 will be provided, if applicable.

4.4.2. Protocol Deviations Due to Disaster or Public Health Emergency

A by-participant listing will be provided for participants with protocol deviations related to COVID-19 (if applicable). The listing of protocol deviations due to COVID-19 (IPDs and non-IPDs) will include a column to specify whether the protocol deviation is an IPD.

4.4.3. Missed and Virtual Visits Due to Disaster or Public Health Emergency

A by-participant listing of participants with missed or virtual visits due to COVID-19 will be provided.

Missed or virtual visits due to COVID-19 are collected on the Visit Date eCRF.

4.4.4. Adverse Events Due to Disaster or Public Health Emergency

AEs of COVID-19 will be included in analyses of AEs if applicable, and will be determined through a COVID-19 Standardized MedDRA Query (SMQ) narrow search.

A by-participant listing of AEs of COVID-19 will be provided.

5. BASELINE CHARACTERISTICS

5.1. Demographics and Baseline Characteristics

Participant demographic variables (i.e., age on Day 1, sex at birth, race, and ethnicity) and baseline characteristics (body weight [in kg], height [in cm], body mass index [BMI; in kg/m²]) will be summarized separately for each participant population and be displayed by treatment group (active participants within each cohort followed by all participants [within population] assigned to placebo) and overall for the population, using descriptive statistics for continuous variables and using number and percentage of participants for categorical variables. The summary of demographic data will be provided for the Safety Analysis Set.

A by-participant demographic listing, including the informed consent date, will be provided separately for each participant population.

5.2. Baseline Disease Characteristics (Virally Suppressed CHB Participants)

Baseline disease characteristics for virally suppressed CHB participants (Cohorts 5 to 7) include:

- years since HBV diagnosis
- HBsAg (IU/mL)
- HBsAg (\log_{10} IU/mL)
- HBsAg Category (≤ 2 , > 2 to < 3 , ≥ 3 to < 4 , or ≥ 4 \log_{10} IU/mL)
- HBsAb Category (< 5 or ≥ 5 mIU/mL)
- Hepatitis B Core Total (Positive, Negative)
- HBV DNA Category ($<$ LLOQ [with subcategories for “ $<$ LLOQ target not detected” and “ $<$ LLOQ target detected”] or \geq LLOQ [with subcategories for “10 to $<$ 69 IU/mL” and “ \geq 69 IU/mL])
- HBV genotype (provided by the Gilead Clinical Virology Group)
- HBeAg Qualitative (Positive or Negative)
- HBeAb Qualitative (Positive, Negative, or Equivocal)
- ALT (U/L)
- ALT Category (\leq ULN or $>$ ULN) using Central Laboratory criteria

- ALT Category (\leq ULN or $>$ ULN) using AASLD criteria (ie, ULN of 35 U/L for males; 25 U/L for females)
- eGFR (mL/min) estimated by Cockcroft-Gault formula
- Prior Interferon

Note: If only the month and year are collected for “date of HBV diagnosis” the day will be set to ‘01’ when imputing the full date. If both the day and month are missing, then ‘01 July’ will be used for the day and month unless the full imputed date is after the first dose date of study drug. If HBV diagnosis date is imputed to be after the first dose date of study drug, set the imputed HBV diagnosis date to the date of first dose of study drug to avoid having a negative duration. The formula to calculate years with HBV disease is as follows:

Duration of HBV Disease (years) =

$(\text{First Dose Date of study drug} - \text{Date of HBV Diagnosis} + 1) / 365.25$

A by-participant listing of baseline disease characteristics will be provided for virally suppressed CHB participants (phase 1b).

5.3. Medical History

General medical history will be coded. A by-participant listing of medical history data will be provided.

6. IMMUNOLOGIC (BOTH POPULATIONS) AND OTHER ANALYSES IN VIRALLY SUPPRESSED CHB PARTICIPANTS

6.1. Secondary Immunologic Endpoint (Phase 1a and Phase 1b)

The incidence and magnitude of vaccine-induced T-cell response will be evaluated for the Immunogenicity Analysis Set and will be based on results from the IFN- γ ELISpot assay.

Immunogenicity will be evaluated using the IFN- γ ELISpot assay with a readout of spot forming cells (SFCs) per 10^6 PBMCs. This assay will be performed using stimulation with 4 overlapping HBV peptide pools (HBV core, HBV Pol A, HBV Pol B, and HBV sAg) that span the bivalent immunogen sequence. All 4 HBV peptide responses will have their value at a visit (mean of 3 replicates) background subtracted using the average unstimulated response (DMSO in triplicate) at the visit. Total vaccine-induced HBV-specific T-cell response will be calculated by adding the response to the 4 peptide pools. An individual participant will be classified as having a T-cell response on IFN- γ EliSpot assay if they exhibit a $\geq 3x$ increase in total vaccine-induced HBV-specific T-cell response over their baseline value at peak (maximum postbaseline value). Participants who have missing values for fold change from baseline will be counted as failures.

The number and percentage of participants with a postbaseline HBV-specific vaccine-induced T-cell response on IFN- γ EliSpot assay will be presented separately for each population (healthy participants and virally suppressed CHB participants) by treatment group (active participants within each cohort followed by all participants [within population] assigned to placebo).

Separate 8-number summaries for the absolute total T-cell response (SFC/ 10^6 PBMCs), change from baseline in total T-cell response (SFC/ 10^6 PBMCs), and X-fold increase over the result at baseline for the peak (highest value postbaseline) HBV-specific vaccine-induced total T-cell response (for each participant) measured using the IFN- γ ELISpot assay will be presented separately for each population (healthy participants and virally suppressed CHB participants) by treatment group.

A stacked bar plot using a different color (or shade of gray [when photocopied] ranging from white to black) to represent the contribution of each of the 4 HBV peptide pools to the total vaccine-induced HBV-specific T-cell response (SFC/ 10^6 PBMCs) will be produced for each of the 2 populations by treatment group. A spaghetti plot of the fold change from baseline by visit in total vaccine response will be created for each population by treatment group.

A listing of the average DMSO-adjusted IFN- γ ELISpot data for each of the 4 HBV peptides and the total for each participant at each visit will be provided. Separate listings will be produced for the 2 participant populations.

The analyses for other exploratory biomarker endpoints listed in the protocol will be described in a separate biomarker analysis plan (BAP).

6.2. Exploratory Analysis of Immune Response to Hepatitis B in Healthy Participants (Phase 1a)

A summary of antibody to HBsAg (mIU/mL) and change from baseline by visit will be summarized for healthy participants assigned to active treatment within each cohort (1, 2, 3, 4, and 8) and for healthy participants assigned to placebo for the Safety Analysis Set.

A listing of HBsAg (qualitative), antibody to HBsAg (mIU/mL), and Hepatitis B core antibody (qualitative) will be provided for healthy participants.

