6.4.5. Clinical Laboratory Tests/Assessments

Blood and urine samples for safety evaluations will be collected throughout the study as outlined in [Table 1](#), [Table 2](#), and [Table 3](#).

No fasting or alteration of diet is required for this study, with the exception of fasting prior to the collection of laboratory assessments performed for screening. Participants should be instructed to fast (no food or drink, except water), starting from midnight (00:00) or earlier, as appropriate, on the evening prior to the screening visit to ensure an approximate 8 hour fast prior to the fasted blood sample collection the next morning.

Table 10. Laboratory Analytes

Safety Laboratory Measurements			
Chemistry (Serum or Plasma)	Hematology	Urinalysis	Other Laboratory Measurements
ALP	CBC with differential, and platelets	Color and clarity	Serum pregnancy test
AST		Specific gravity	Urine pregnancy test
ALT		pH	Serum FSH
GGT	Coagulation panel, including prothrombin time, aPTT, and INR	Glucose	Plasma HBV DNA, HBV RNA, HBV surface antigen
Total bilirubin		Protein	HBV surface antibody
Direct and indirect bilirubin		Blood and microscopic (reflex if positive)	HBV core-related antigen
Total protein		Leukocyte esterase and microscopic (reflex if positive)	HBeAg
Albumin			HBeAb
Lactate dehydrogenase			HIV serology
Bicarbonate			HDV antibody
BUN			HCV antibody serology reflex to HCV RNA
Calcium			HBV immunogenicity (IFN- γ ELISpot assay)
Chloride			HBV-1-specific T-cell phenotype and function
Creatinine			Peripheral soluble proteins (including cytokines, chemokines, and inflammatory markers)
Glucose			Antivector immune responses
Hemoglobin A1c			Autoantibodies: ANA, anti-SMA, AMA, and anti-TPO
Phosphorus			
Magnesium			
Potassium			
Sodium			
Lipase			
Total cholesterol			
High-density lipoprotein			
Low-density lipoprotein			
Triglycerides			
CPK/CK			
Uric acid			

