8.3.2. Data Handling Conventions

Laboratory data that are continuous in nature but are less than the LLOQ or above the upper limit of quantification will be imputed to the value of the lower or upper limit minus or plus 1 significant digit, respectively (eg, if the result of a continuous laboratory test is less than 20, a value of 19 will be assigned; if the result of a continuous laboratory test is less than 20.0, a value of 19.9 will be assigned).

Missing data can have an impact upon the interpretation of the study data. In general, values for missing data will not be imputed. However, a missing pretreatment laboratory result would be treated as normal (ie, no toxicity grade) for the laboratory abnormality summary.

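### SAP 6.1 defines T-cell response as a 3-fold rise over a background-subtracted baseline that can be zero or negative, with no floor, so the rule gives no valid classification there and accepts trivial rises just above zero

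*SAP*

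**What the plan says.** SAP 6.1 builds the endpoint in three steps.

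- Each of four HBV peptide-pool readings (mean of three replicates) is "background subtracted using the average unstimulated response (DMSO in triplicate) at the visit".
- The four subtracted readings are added to give the total response.
- A participant is a responder on a 3-fold or greater "increase in total vaccine-induced HBV-specific T-cell response over their baseline value at peak (maximum postbaseline value").

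The section then adds one rule for incomplete data: "Participants who have missing values for fold change from baseline will be counted as failures".

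Two other outputs use the same ratio: a summary of the "X-fold increase over the result at baseline for the peak (highest value postbaseline") and "A spaghetti plot of the fold change from baseline by visit in total vaccine response". Three do not: the summary of the absolute peak total, the summary of change from baseline, and the participant listing that begins "A listing of the average DMSO-adjusted".

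SAP 6.1 does not say what happens when the baseline total is zero or negative, whether pools are truncated at zero, or whether a minimum peak or rise is needed. Protocol 8.6 names the proportion with a response but gives no cut-off.

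**The concern.** A ratio needs a denominator safely above zero. Here the denominator is a difference between noisy readings, taken from the single Day 1 pre-dose sample (Protocol Tables 4 to 6). The numerator is the largest of 7, 9 or 10 postbaseline values, depending on cohort.

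Two faults follow. For a baseline of zero or below, the classification depends on how the rule is programmed, and the two obvious codings err in opposite directions. For a baseline just above zero, a rise of a few spots is enough.

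Incidence of response is one of the two parts of the only secondary endpoint. With 8 active participants per cohort, a few wrong classifications visibly change the displayed rate. The incidence table could also contradict the listing behind it.

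**Working it through.** **Structure of the total.** Total = (P1 − D) + (P2 − D) + (P3 − D) + (P4 − D) = (P1 + P2 + P3 + P4) − 4D, where P is a pool mean and D the DMSO mean at that visit. Nothing keeps this above zero.

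**Applying the rule by hand (SFC/10^6; no assay assumption needed).**

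| Baseline | Peak | Peak/baseline | Fold reading | Coded peak ≥ 3 × baseline |
|---|---|---|---|---|
| 0 | 500 | undefined | failure (missing fold change) | responder |
| −5 | 500 | −100 | failure | responder |
| −2 | −1 | 0.5 | failure | responder |
| −2 | −6 | 3.0 | responder | responder |
| 2 | 6 | 3.0 | responder | responder |
| 200 | 550 | 2.75 | failure | failure |

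If a 3-fold increase over baseline means a rise of three baselines (a peak of four), then 2 to 6 fails but 2 to 8 passes.

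**Whether other text repairs it.**

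- Protocol 8.3.2 has an imputation rule for "Laboratory data that are continuous in nature but are less than the LLOQ", and Protocol Table 10 lists "HBV immunogenicity" by ELISpot among the analytes. No ELISpot LLOQ is given, nor whether imputation would come before or after subtraction.
- SAP 3.7 covers results reported as below or above a limit, not computed differences. SAP 3.6.1 imputes nothing further.
- Protocol 8 also points to a biomarker analysis plan, but SAP 6.1 assigns it only the other exploratory endpoints.

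**Weight of one participant.** Active cohort: 1/8 = 12.5 points. Pooled Phase 1a placebo: 5 cohorts × 2 = 10, so 10 points. Pooled Phase 1b placebo: 3 × 2 = 6, so 16.7 points.

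**Illustration of frequency.** The documents give no assay settings, so these are assumed: 1, 2 or 3 × 10^5 cells per well; background 2, 5, 10 or 20 SFC/10^6; Poisson counts; 7, 9 or 10 postbaseline visits (counted from SAP Table 3-3); a true rise of 300 held at every visit, or none.

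The noise variance of the total at a true value of zero is (4 + 16)/3 × background × 10^6/cells. The 16 arises because D is subtracted four times. The noise SD is:

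- smallest: √(20/3 × 2 × 10^6/300,000) = 6.7
- largest: √(20/3 × 20 × 10^6/100,000) = 36.5

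Share scored as responders, pools untruncated, with the floor F set at one noise SD:

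| True baseline | Rule | True rise of 300 | No true change |
|---|---|---|---|
| 0 | fold reading | 50–53% | about 13–18% |
| 0 | peak ≥ 3 × baseline | above 99.9% | about 61–68% |
| 0 | floored | at least 99% | at most 0.6% |
| 20 | fold reading | 70–99% | 11–26% |
| 20 | floored | at least 99% | 2–25% |
| 50 | fold reading | 88–100% | 0.3–24% |
| 50 | floored | at least 99% | 0.3–22% |

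Truncating each pool at zero does not cure the fold reading. At true baseline 0, it scores 64–77% of true rises of 300 and 19–37% of unchanged participants, because negatives become exact zeros or small positives.

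A floor can also raise false responders. With 200,000 cells per well, background 20, true baseline 30 and 10 visits, a floor of 20 takes them from 26% to 32%; a floor of 50 takes them to 0%.

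**The case against.** A reader might infer that the plan scores every strong responder with a baseline of zero or below as a failure, and so understates response. The documents do not support that as a settled result. SAP 6.1 never says that a zero denominator counts as missing and is silent on negative baselines. The fold reading is the natural one because the section speaks of fold change, but the multiplicative coding errs the other way. What stands is that the classification is not validly defined, with the direction of error depending on the coding.

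A reader might also take the 50–53% as a forecast for Phase 1a, whose participants have no prior HBV infection. That is not supported either. No document reports baseline ELISpot levels. Protocol 4.2.2 excludes HBV vaccination only within 12 months of screening, so earlier vaccinees can enrol, and surface antigen is one of the four pools. Phase 1b participants are chronically infected. At higher true baselines far fewer responders are missed.

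The consequence is limited, and this objection stands in full. SAP 3.5 rules out formal testing, escalation rests on safety data, and a participant going from 0 to 500 is plain in the absolute and change summaries and the listing. A reader could recompute the classification. The laboratory may already truncate or floor its results, but neither document says so.

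**Conclusion.** The point holds as a gap in the responder definition. For a baseline of zero or below the rule gives no valid classification, and for a small positive baseline it accepts a trivial rise. Both conclusions follow from the SAP text and arithmetic alone.

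How many participants are affected cannot be known from the documents. The simulated percentages rest on assumed assay settings and on the coding, and serve only to show that the effect can be large when true baselines are near zero. The damage is confined to the incidence table, the fold-change summary and the spaghetti plot of a descriptive endpoint. It should be fixed because incidence is half of the only secondary endpoint and the groups are small. It does not undermine the primary safety objective or the absolute immunogenicity results.

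**What to change.** In SAP 6.1:

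1. Set a floor F for the total from assay validation or pre-dose DMSO data, and state whether pools are truncated at zero.
2. Define a responder as peak total ≥ 3 × max(baseline, F). This also settles whether the threshold is three or four times baseline.
3. Use max(value, F)/max(baseline, F) in the fold-change summary and spaghetti plot, so that they agree with the responder table.
4. Count missing as failure only when a participant has no baseline ELISpot result.

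Fix F before postbaseline ELISpot results are examined by treatment. Finalising the SAP before database finalisation (SAP 1) is not enough, because some sponsor personnel are unblinded (Protocol 5.1.2) and interim analyses are allowed at the sponsor's discretion (SAP 2.1). Pre-dose data carry no treatment information. If postbaseline results have already been seen, say so in the study report and show the as-written and floored rates side by side.

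The cost is SAP wording and derivation code, with no new samples. F must be justified, and it implies a minimum peak of 3F. It does not remove false responders when the true baseline is well above F, and can raise them slightly, because one noisy baseline is still compared with the maximum of 7 to 10 visits.
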